1.0 INTRODUCTION

1.1 Background

The exchange of relevant clinical information from one provider to another is crucial for the surgical pathway (Nagpal et al., 2012). Structured and precise communication is essential for good cooperation between health care providers to avoid necessary information get lost (Haig et al., 2006; Leonard et al., 2004). Missing information and incorrect data transfer can lead to adverse patient outcomes (Nagpal et al., 2012). Poor communication among health care providers has been identified as the third leading root cause of sentinel incidents (The Joint Commission, 2016). Although there is limited high-quality research investigating whether handover techniques have an impact on patient-related outcomes in nursing care (Bukoh & Siah, 2020; Rosenthal et al., 2018), structured handovers are effective in reducing the number of mistakes in information transfer (Bukoh & Siah, 2020; Müller et al., 2018).

Different types of structured communication tools have been developed for handover (Bukoh & Siah, 2020; Mardis et al., 2016). The Information-Situation-Background-Assessment-Recommendation (ISBAR) instrument provides a method for consistent, structured communication between healthcare providers (Müller et al., 2018). ISBAR was introduced by airline crew programs for effective team communication and was later adopted by the hospital in 2002 at Kaiser Permanente of California as part of fostering a culture of patient safety (Haig et al., 2006). The ISBAR approach constitutes a generic, transferable non-technical skill (McCabe & Timmins, 2013), also needed in inter-and interprofessional collaboration with patients who undergo surgery (Kitney et al., 2018; Kitney et al., 2016; Nilsson et al., 2020). The goal of ISBAR is to achieve increased patient safety by providing necessary and accurate information. Through a structured communication, the participants can share the same mental models when caring for patients (Shahid & Thomas, 2018). ISBAR can improve communication (Jeong & Kim, 2020; Raurell-Torredà et al., 2021) and reduce communication errors (Randmaa et al., 2014). ISBAR is used as a communication tool in Norway today (Helsedirektoratet, 2020) and is an integrated part of the curricula in nursing education.

Earlier studies investigating the effect of structure communication through the ISBAR approach have mainly investigated satisfaction among the users (Müller et al., 2018). Few studies have investigated the effectiveness of teaching methods (Jeong & Kim, 2020). A systematic search done for this project identified one RCT study (Raurell-Torredà et al., 2021), one single-blinded randomized control pretest-posttest study (Jeong & Kim, 2020), and one randomized posttest with a comparison group (Lanz & Wood, 2018). Thus more studies are needed.

Communication tools like ISBAR can also be learned using digital technology as emphasized in the Norwegian Government Digitalization Strategy for the university and college sector 2017-2021 (The Norwegian Ministry of Education and Research, 2017): “through digitalization, new opportunities will be created for new and changed learning and teaching processes” (p. 5). One example is desktop virtual reality (VR) which is a three-dimensional computer environment where the users can interact with an environment displayed on a

computer monitor with a mouse, keyboard, and a screen on a computer/laptop/tablet (Shorey & Ng, 2020).

Desktop VR is typically built around user interaction, such as typing commands and interacting with others in the group-practicing. The advantage of desktop VR is the potential for letting users practice without supervision while receiving audio and visual instruction and instant feedback from the VR itself in a safe environment (Shorey & Ng, 2020). The development of active learning forms through desktop VR aligns with research studies recommending interactive teaching strategies curricula (Horntvedt et al., 2018). COVID-19 and resulting campus lockdowns have created challenges for nursing students' learning opportunities (Morin, 2020; Ulenaers et al., 2021). Increased numbers of nursing students being educated in nursing programs also show the need for effective and practical group-based learning in nursing education programs.

Previous, a version of the ISBAR web application has been developed by members of the research group for this project (www.virsam.no). In this project a Preoperative ISBAR desktop VR will be built based on this existing version. The pedagogical approach is based on the student-centered theory of *Constructive alignment* (Biggs, 2001). *Constructive* refers to the theory that the students construct meaning through relevant learning activities and *alignment* refers to the teaching and learning situation. Alignment is achieved when the designed learning activity is devised to fit the learning outcome and the assessment (Biggs & Tang, 2007). The Preoperative ISBAR desktop VR is thus developed to address the need for effective student-centered learning.

Usability is an essential component of good practice in developing a product (Rubin & Chisnell, 2008). The International Organization for Standardization has defined usability as “the extent to which a product can be used by specified users to achieve specified goals with effectiveness, efficiency and satisfaction in a specified context of use” (Bevan et al., 2016). Systems should be intuitive and easy to use for the end-users, and perceived usability is an essential determinant for successful implementation (Rubin & Chisnell, 2008). Thus, investigating the usability is a central part of developing The Preoperative ISBAR desktop VR.

1.2 Aims of the project

This project is part of the larger research project “Learning activities for undergraduate nursing students who are learning pre- and postoperative nursing”. In the larger research project, a scoping review has been conducted to systematically map and summarize learning activities for undergraduate nursing students who are learning pre- and postoperative nursing prior to clinical placement (Andreasen, Slettebø & Opsal, 2021, in review). This work, together with the project described in this protocol, will constitute a PhD project.

The overall aim of the project described in this protocol concerns the development and testing of the effect of a desktop VR application to practice ISBAR communication along a

preoperative patient pathway. This will be investigated in two studies with the following aims:

1. To describe the development of a desktop VR application to practice preoperative ISBAR communication and evaluate the usability. The specific research question is: *What are the number, type and severity of usability issues evaluated by second-year nursing students in terms of effectiveness, efficiency and satisfaction?*
2. To investigate the effect of a desktop VR application to practice preoperative ISBAR communication compared to traditional teaching methods. The specific research question is: *Does practicing preoperative ISBAR approach in a web application provide a non-inferior learning outcome compared to a traditional group practicing for second-year nursing students?*

2.0 METHODS

To answer the research questions, two different studies will be conducted, a qualitative study (aim 1) and a randomized controlled trial (aim 2)

2.1 Qualitative study (aim 1 - usability)

2.1.1 Study design

This study has a qualitative study design with two interlinked activities.

Activity 1 includes developing the Preoperative ISBAR on desktop VR based on the already existing ISBAR Web Application (prehospital version from www.virsam.no). This will be done iteratively along with the usability tests, and in continuous dialog within the research group and between the research group and the programmer.

A report from Immersive Healthcare Collaboration (2020) has highlighted three aspects which is lacking in the development of immersive healthcare training. These aspects have been considered in when designing this project. Firstly, design and development have been driven by learning needs. Secondly, implementation will go together with rigorous evaluation, and lastly, collaboration have been fostered to ensure efficient and effective use of immersive technology.

In activity 2, end-users will test the usability of Preoperative ISBAR on desktop VR. The methodological method used will be think-aloud, questionnaire, and student interviews. These methods will be suitable for collecting data on the students' practical use of Preoperative ISBAR desktop VR and providing insight into usability issues.

The study design ensures that the end-users are actively involved in the development stage before the solution is used in the randomized controlled trial to test the learning outcome of the Preoperative ISBAR desktop VR with a larger sample of participants (aim 2).

2.1.2 Participants and recruitment

Activity 1: The main participants will be the research group and the programmer. In addition, an expert panel will be used in the content revision process of the ISBAR web application. Three nursing teachers, two doctors, and one nurse will be asked to join an expert group and give their opinions about the web application and proposed changes. They will be recruited through the network of the research group members, ensuring that those recruited do not have any impartiality issues with the members of the research group.

Activity 2: The aim is to include second-year nursing students. The recruitment of students will be done at the Department of Health and Nursing Science at the University of Agder, Norway. The participants will be nursing students in their second study year. A purposeful sample of ten participants is considered adequate for robust usability testing (Virzi, 1992). Still, as the training is organized in groups of three, nine will be the number of participants. Recruitment will be purposive sampling to ensure variation in age, gender, and anticipated digital competence. A variety of students can enhance the generalizability of results (Rubin & Chisnell, 2008).

2.1.3 Data collection

In activity 1, the data collected will consist of notes from the meetings in the research group and with the programmer, and the meetings in the expert panel. The focus of the data collection will be on the arguments used for suggesting and deciding on the chosen solutions.

In activity 2, The data collection will be conducted accordingly to (1) the think-aloud method, (2) the questionnaire, and (3) a focus group interview, as described in detail below.

Think-aloud method

Think-aloud is a research method in which participants speak aloud any words in their mind as they complete a task and provide a valuable source of data about participant thinking (Charters, 2003). Each training participant will be placed in a separate room with a researcher collecting the data during a predefined task. First, the researcher will ask background questions about age, gender, comfort with technology and knowledge about ISBAR (Appendix 1). Secondly, the participants will be encouraged to think aloud, i.e., to verbalize their thoughts and respond to the tasks constantly. If the students are unsure how to proceed, they will be encouraged to do what they will find most intuitive before being assisted by the researcher. Data will be collected by three researchers observing the students as they use the desktop VR. Filed notes will be made based on a predefined observation template covering navigation errors, ease of use, apparent misunderstandings, or technical difficulties (Appendix 1). Each think-aloud session will be video recorded. After task completion, each student will take part in a questionnaire.

Questionnaire

The System Usability Scale (SUS) questionnaire (Bangor et al., 2009) will evaluate user satisfaction and comprises 11 open-ended questions (Appendix 2). The average scores will be categorized based on ratings.

Focus group interview

After the think-aloud session and questionnaire, the participants from the same group will gather in a room and participate in a focus group interview. An interview guide explicitly designed for this study will be followed (Appendix 3), systematically developed based on the research question and usability theory (Castillo-Montoya, 2016; Rubin & Chrisnell, 2008). The interview will also address specific usability issues that will be observed when the participants did the predefined task. The same guide will be followed for all participants. The interview sessions will be audio recorded.

2.1.4 Analysis

Descriptive statistics measured from the think-aloud session and data from the SUS questionnaire will be categorized in IBM SPSS Statistics for Windows, version 27 (IBM Corp). Qualitative data from the focus group interviews will be transcribed verbatim and NVivo for Windows (QSR International Pty Ltd, version 18, 2021) will be used for managing the transcript data. Qualitative data will be analyzed using deductive content analysis (Elo & Kyngäs, 2008). Collected data will be coded according to the predefined categories. Predefined categories are usability issues in terms of effectiveness (task completion, navigation errors, ease of use, apparent misunderstandings, technical difficulties), efficiency (fatigue), and satisfaction (Bevan et al., 2016). Each issue will be graded on a scale from 1 to 4 (1 = irritant, 2 = moderate, 3 = severe, and 4 = unusable) (Rubin & Chisnell, 2008). The grading will be done by two of the authors ([name]) and independently and subsequently discussed until consensus will be reached on each issue of divergence.

2.2 Randomised controlled trial (aim 2 – effect)

2.2.1 Study design

The study design will be a non-inferior, parallel-group randomized controlled trial (RCT). As web applications may have some disadvantages compared to real-life skill practice, the study will be conducted as a non-inferior study (Piaggio et al., 2012). The *Reporting of Noninferiority and Equivalence Randomized Trials. Extension of the CONSORT 2010 statement* (Piaggio et al., 2012) have been used to guide the design phase and will be used

throughout the reporting process. The study will be registered in www.clinicaltrials.gov before data collection for the RCT is started.

2.2.2 Participants and recruitment

The inclusion criteria will be second-year nursing students at one of the two campus sites of the Faculty of Health and Nursing Sciences, University of Agder.

The students will be informed both oral and written a week before and at the start of the session. The students who attend the session will be eligible and those who consent will be included in the study.

2.2.3 Randomization and allocation

The participants will take part in a teaching program integrated into their curriculum. As a part of this study, they will be randomized into groups of three who then are randomized to take part in two different types of practicing the ISBAR approach. The group size of three is based on earlier studies reporting no difference in performance between groups of three, four, or five (Rezmer et al., 2011).

The participants will be organized in groups of three with a predefined group number that will be given to them before they start practicing.

Randomization will consider the practical organization of the teaching, which includes batches of students which must be allocated at separate times. For randomization, separate lists will be prepared for each batch using the Microsoft Excel RAND function. The lists will be printed on identifying stickers with identification (ID) numbers and codes for the type of practice in which the students were to participate. The allocation will be done by asking each student entering the classroom to sequentially seat themselves at the desk with the lowest available ID number. They will not be informed about what the allocation codes on their stickers mean.

After the introduction, the participants will be informed about where to go for their training according to the allocation codes on their stickers by the person in charge of the session. The instructors for the self-practice part will not influence the allocation and will ensure that they get students with the correct allocation.

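### The allocation procedure does not secure concealment across batches: arm codes sit on the desk stickers, protected only by withholding their meaning

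*Protocol*

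**What the plan says.** Section 2.2.3 (Randomization and allocation) makes a separate random list for each batch, because the batches are taught at different times. Each list is turned into "identifying stickers with identification (ID) numbers and codes for the type of practice". Students entering the room are asked to "sequentially seat themselves at the desk with the lowest available ID number". On masking, the section says: "They will not be informed about what the allocation codes on their stickers mean". Once the introduction is over, "the participants will be informed about where to go for their training according to the allocation codes on their stickers". The section adds that the self-practice instructors have no influence on allocation.

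Section 2.2.4 (Interventions) makes the two destinations easy to tell apart. VR participants go to separate rooms with their own computers; control participants stay in trios with a printed case.

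Section 2.2.2 (Participants and recruitment) provides information a week ahead and again when the session starts. On inclusion it says: "The students who attend the session will be eligible and those who consent will be included in the study". It gives no time for consent relative to seating.

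**The concern.** Allocation concealment requires that nobody who can affect entry or order knows the next assignment before it is taken up. Here the assignment is physically present at the desk, in coded form, when the student arrives. What keeps it concealed is ignorance of the code.

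That ignorance ends in every session, when the code decides which room a student goes to. This does no harm to the batch concerned, which is already seated. It matters for batches that come later, because they are second-year students of the same faculty and may hear what the codes meant. If the labels are unchanged and legible, the arm of the lowest free desk can be read off before it is taken.

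A student who prefers one form of practice could then let someone else go ahead, or could decline to take part. Either would make arm membership depend on preference, and perhaps on digital confidence or skill. The non-inferiority comparison relies on randomisation to balance these.

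**Working it through.** The plan has no figure for concealment, so the main check sets the stated steps side by side and asks what each one secures.

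| Step (Protocol section) | What it secures | What it leaves open |
|---|---|---|
| Separate random list per batch (2.2.3) | One batch's sequence does not predict the next | Whether the code labels differ between batches |
| ID number and arm code on one sticker (2.2.3) | Student and assignment are linked | Whether the code is covered or legible before sitting |
| Lowest available ID on entry (2.2.3) | No free choice of desk | Place in the queue; whether to take part |
| Meaning of codes withheld (2.2.3) | Concealment while the meaning is unknown | What holds after an earlier batch has been sent out by code |
| Instructors do not influence allocation (2.2.3) | Self-practice instructors | Students themselves |
| Information a week before and at the start (2.2.2) | Consent before seating is possible | Whether consent actually comes before seating |

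Separate lists do not close the gap. An unpredictable sequence protects only when the next assignment cannot be seen. If the label is on the desk and its meaning is known, nothing has to be predicted.

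For a later batch to be affected, four things must hold: the labels are reused, their meaning is passed on, the code can be read before sitting, and a student acts on it. The protocol states none of these and excludes none of them.

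**Can the effect be sized?** Inputs from section 2.2.7: margin 13 points, expected success 20%, power 80%, alpha 0.05, 118 per group, 250 in total. The plan's figure reproduces with one-sided alpha:

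n = (1.645 + 0.842)² × (2 × 0.20 × 0.80) / 0.13² = 117.1, rounded up to 118 per group.

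For 125 per arm (250 / 2), take non-inferiority as declared when d − 1.645 × SE > −0.13. Here d is the VR minus control proportion and SE is the unpooled standard error. The probability is the sum, over all pairs of binomial counts that meet the rule, of the product of the two binomial probabilities. Control is held at 20%. The shifts in the VR rate are assumed, not taken from the protocol.

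| True VR rate without bias | Assumed shift | P(declare non-inferiority) |
|---|---|---|
| 7% (at the margin) | 0 | 5.6% |
| 7% | +1 point | 8.7% |
| 7% | +3 points | 17.5% |
| 7% | +5 points | 29.7% |
| 7% | −3 points | 1.1% |
| 20% (equal) | 0 | 82.5% |
| 20% | −3 points | 65.9% |

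The table shows only that the test is sensitive to shifts of a few points, in either direction. It does not estimate the bias in this trial.

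**The case against.** The strongest reply is that the protocol describes no actual breach. Desks are found by ID number, and the text does not say the code is legible from the aisle. Consent may well be collected before anyone sits. New labels for each batch may already be the practice. Telling students their arm after they are seated is unavoidable and is no leak in itself. The lowest-ID rule takes away choice of desk, and a seat swap would breach the procedure.

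Much of this stands, and it rules out several stronger readings that a reader might infer:

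- **That students see their arm before sitting and before consenting, so concealment fails after the first batch.** Legibility, reuse of labels and the timing of consent are all unstated. The text supports only that concealment is not secured.
- **That friends can form trios by arriving together.** This needs trios to follow consecutive ID numbers. The protocol does not say so; it says students are randomised into their trios.
- **That false non-inferiority rises to 17% or 30%.** These values come from assumed shifts of 3 and 5 points. They apply the shift to every VR student, including the first batch, and hold control fixed although sorting would normally move both arms. They also show only the direction that favours VR. If stronger students preferred group practice, the bias would run the other way.

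What does not stand is the idea that the existing safeguards are enough. The seating rule does not govern when a student joins the queue or whether the student consents. Per-batch lists change the sequence, not necessarily the labels. The statement about instructors does not cover students.

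**Conclusion.** The point holds as a gap in the stated procedure. Section 2.2.3 puts the arm code at the desk and relies on withheld meaning, and then acts on that code in each of several batches allocated at separate times. No stated step keeps later batches from knowing the code, and section 2.2.2 does not put consent ahead of seating.

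Whether any bias would follow depends on the four unstated conditions above. Its size and direction cannot be derived from the protocol. Severity is low to moderate. It is worth acting on because the remedy is cheap and because selection at allocation cannot be undone by analysis afterwards.

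**What to change.** Rewrite sections 2.2.2 and 2.2.3 as follows:

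1. Print only the ID number on the stickers.
2. Record consent before the allocation is revealed, and say so.
3. Have the person in charge hold each batch's list linking ID to trio and arm, and open it only after consent has been recorded, at the end of the introduction.
4. If codes must stay on the stickers, use a new random code set for each batch.

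The cost is reprinted stickers and a look-up of a few minutes per batch when students are sent to their rooms. No extra staff or participants are needed, and the sample size does not change.
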